Proof of Concept: A Commode
Assist Device for Excessive
Perineal Descent

NCT# 02419924

June 01, 2016

IRB proposal

June 1, 2016

Proof of Concept: A Commode Assist Device for Excessive Perineal Descent

Background: Constipation is a common gastrointestinal disorder, affecting 15-30% of the population. The incidence increases with age, childbearing, chronic constipation, and with chronic illness. It is associated with high healthcare costs, depression and reduced quality of life. A laxative is prescribed for nearly every office visit for constipation. A common type of constipation seen in tertiary care centers is called outlet obstruction – or pelvic floor dysfunction, which is diagnosed by tests not typically available in community hospitals or the clinical practice setting. Standard and magnetic resonance defecography, done to identify contributing causes of constipation, identifies excessive perineal descent. Excessive descent results from extreme laxity of the pelvic floor muscles, leading to refractory evacuation. While many outlet obstruction disorders respond to treatments, excessive perineal descent is a condition for which there is no known medical or surgical treatment. Standard treatments for pelvic floor disorders like strengthening exercises do not improve constipation nor raise or brace the perineum. Surgery cannot provide adequate support nor repair these weak muscles.

Aim: To address this common problem, in collaboration with [name], [name], and more recently Mayo Clinic mechanical bioengineers [name] and [name], a pelvic floor support device has been designed, and is ready to be tested. Testing involves comparing perineal descent during standard defecography to descent with the device in place. Radiation exposure is brief and low level.

Sample size: A proof of concept study is proposed to evaluate the feasibility of the CAD for patient use, effectiveness, and satisfaction. A sample size of 16 patients randomly, counterbalanced to both standard toilet seat and CAD was considered sufficient to evaluate potential for further study of the current version of the CAD device.

Methods: The study would include standard defecography using the standard commode (simulates normal toilet seat) under fluoroscopy using barium paste (180 ml) instilled in the rectum and five standard radiographic spot films including images at rest, with squeeze, with strain, during evacuation and post-evacuation. The patient would have additional barium paste (same quantity) instilled in the rectum for a repeat exam (same 5 spot radiographs) using the commode assist device.

Analyses: The standardized commode would serve as the control and be compared with commode assist device for differences in anorectal angle, perineal descent, and rectal emptying during the clinical maneuvers at rest, with squeeze, and with straining. Additionally, patients will complete a short Likert scale questionnaire rating sense of straining, ease of evacuation, and completeness of evacuation for each condition. Statistical comparisons will be completed using non-parametric Wilcoxon signed-rank test for repeated measurements. However, determination of sufficient efficacy for further study and potential redesign will be based on expert opinion of clinical observations.

Risks: All procedures are the standard of practice at Mayo Clinic Arizona. The radiation used for the additional exam is considered very low, and should not present a hazard to patients (see attachment for dosimetry from medical physics). Premenopausal women would be required to have a urine

pregnancy test, and if positive would be excluded from the study as is required by our standard clinical protocols.

Summary: Excessive perineal descent is an underdiagnosed, common cause of constipation. This is a medical problem for which no known treatment exists. The concept of a support device has been received well by patients with the disorder. At present, the condition is diagnosed only at tertiary medical centers that have special diagnostic equipment. A support device that fits onto any toilet is a cost effective, safe and efficacious solution to a common and difficult problem. This has substantial marketability.

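### The Sample size paragraph promises random counterbalancing of the two exams, but Methods describes only one sequence, with the device exam as the repeat; followed as written, device and exam order are confounded.

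*Combined protocol and SAP*

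**What the plan says.** The combined protocol and SAP addresses exam order, directly or by implication, in four places.

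- **Sample size:** "A sample size of 16 patients randomly, counterbalanced to both standard toilet seat and CAD". No ratio, block size or method of assignment is given.
- **Methods, standard exam:** "The study would include standard defecography using the standard commode (simulates normal toilet seat) under fluoroscopy using barium paste (180 ml) instilled in the rectum", with five spot films.
- **Methods, device exam:** "additional barium paste (same quantity) instilled in the rectum for a repeat exam (same 5 spot radiographs) using the commode assist device". Randomisation and a device-first path are not mentioned.
- **Analyses:** "Statistical comparisons will be completed using non-parametric Wilcoxon signed-rank test for repeated measurements". Sequence and period are not mentioned. The decision does not rest on this test: "determination of sufficient efficacy for further study and potential redesign will be based on expert opinion of clinical observations".

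Risks also refers to a single extra exam: "The radiation used for the additional exam is considered very low".

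**The concern.** Each patient is examined on both seats and the analysis is paired, so exam order is the only thing left to counterbalance. Methods gives one path, and it attaches both the extra paste and the idea of a repeat to the device alone. Staff working from Methods have no instruction to put the device first for anyone.

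Under that single path, whatever changes between a first and a second exam enters every device-minus-standard difference. Practice, fatigue and paste left from the first exam are all possible sources. The second exam follows an evacuation and a second 180 ml instillation, and the outcomes include rectal emptying and patient ratings of straining, ease and completeness. The bias could flatter the device or hide a real benefit, and it cannot be repaired once the data are collected. Resting the decision on expert opinion gives no protection, because the experts would be judging the same films and ratings.

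**Working it through.** **Is there a conflict?** The documents contain no figure to reproduce here: 16 is declared sufficient without an alpha, power, effect size or SD. The first step is therefore to set the texts side by side.

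| | Sample size | Methods |
|---|---|---|
| Order | random, counterbalanced | not stated as random |
| Standard then CAD | implied for some patients | the only path described |
| CAD then standard | implied for some patients | absent |

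Methods does not use words such as first or second; the sequence is carried by the terms used for the device exam. Nothing else in the document supplies the missing sequence.

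**What would it do? (illustration)** Only n = 16, the pairing and the signed-rank test come from the documents. Everything else is assumed:

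- The paired difference D (CAD minus standard, positive meaning better) is Normal with SD 1.
- The device effect is τ, and the second-exam effect is π, in SD units of D.
- The test is two-sided at 0.05. The exact signed-rank critical region for n = 16 is W ≤ 29 or W ≥ 107, with attained size 4.4%.

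Mean of D:

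- Fixed order, standard first: τ + π for all 16 patients.
- 8/8 counterbalanced: τ + π in eight patients and τ − π in eight, so the average is τ.

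Expected number of patients who look better on an ineffective device (τ = 0):

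- Fixed order: 16·Φ(π). For example, 16 × Φ(0.5) = 16 × 0.6915 = 11.06.
- 8/8: 8·Φ(π) + 8·Φ(−π) = 8.0 for any π.

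Rejection rates with τ = 0 (simulation, 200,000 runs per setting):

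| π (SD) | Look better, fixed order | Signed-rank, fixed order | Signed-rank, 8/8 | Period-adjusted rank-sum, 8/8 |
|---|---|---|---|---|
| 0.25 | 9.6 of 16 | 14% | 3.9% | 5.0% |
| 0.5 | 11.1 of 16 | 43% | 2.5% | 5.0% |
| 0.75 | 12.4 of 16 | 77% | 1.2% | 4.9% |
| 1.0 | 13.5 of 16 | 95% | about 0.5% | 4.9% |

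The rank-sum test compares second-minus-first differences between the two sequences. Their means are π + τ and π − τ, so the contrast is 2τ and π cancels. Its exact critical region for 8 against 8 is W ≤ 49 or W ≥ 87, with size 5.0%.

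**Power for a true benefit of τ = 0.8:**

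- No order effect, signed-rank: 82%.
- Fixed order, π = −0.5 (working against the device): 18%.
- 8/8, π = 0.5, unadjusted signed-rank: 74%.
- 8/8, π = 0.5, period-adjusted rank-sum: 82%.

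**What counterbalancing does not cure.** Suppose the order effect is 0.5 SD after the standard seat and 0 after the CAD, with τ = 0. The remaining bias under 8/8 is (0.5 − 0)/2 = 0.25 SD, against 0.5 SD under fixed order. Rejection is about 12.5% for the unadjusted signed-rank test and 15% for the adjusted test under 8/8, against 43% under fixed order.

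**The case against.** The strongest reply is that the design feature is already in the plan. The Sample size paragraph assigns the order, and Methods merely lists the content of the two exams, with the extra exam meaning extra to usual care, as in Risks. On that reading the only certain defect is that Methods does not restate the sequence, and confounding arises only if staff overlook another paragraph. This reading is possible, and it is why the consequence is stated conditionally. It does not close the gap, because no text gives staff both sequences or tells them how to assign them.

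The order effects are assumed. At 0.1 SD the harm is slight: about 6% rejection under fixed order, and 16 × Φ(0.1) = 8.6 patients looking better. The mechanisms named above bear more plausibly on emptying and the ratings than on perineal descent, the comparison named in the Aim. Rejection rates also matter less when experts decide, and nothing says that they will count patients who improved. These points stand as limits on the size of the problem.

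The rest and post-evacuation films would let experts see leftover paste, though not practice or fatigue.

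Finally, under counterbalancing with an equal order effect, the planned signed-rank test is conservative, not invalid. With π = 0.25 its power for 0.8 SD is 80%, against 82% adjusted, and under unequal carry-over the adjusted test rejects slightly more often. Period adjustment is therefore an improvement, secondary to fixing the sequence.

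**Conclusion.** The concern holds. The two paragraphs conflict on how the exams are ordered, and the one that staff would work from describes a design in which device and order cannot be separated. That conclusion rests on the text alone.

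The size is illustrative. It assumes Normal differences, a two-sided 5% level and order effects from 0.25 to 1.0 SD. On that basis, an ineffective device would be declared different in 14% to 95% of studies under fixed order, and a 0.5 SD effect against the device would leave 18% power for a true 0.8 SD benefit. With 8/8 counterbalancing and an equal order effect, the average bias is zero.

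This should be fixed before enrolment. It is an inconsistency in a proof-of-concept plan that already intends counterbalancing, but the standard-versus-device comparison is the purpose of the study and the damage could not be undone later.

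**What to change.** Reconcile Methods with the Sample size paragraph in one of two ways.

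1. **Keep counterbalancing.** State in Methods that exam order is randomised and balanced, for example 8 standard-then-CAD and 8 CAD-then-standard. Describe both sequences, replace the wording that ties the repeat exam to the device with a statement that the second exam uses the other seat, and record each patient's sequence. In Analyses, report results by sequence and preferably use a period-adjusted paired comparison, such as the rank-sum test of second-minus-first differences between sequences. Give the expert reviewers the results by sequence. Report the first exam's post-evacuation film by sequence as a limited check on paste carried into the second exam; a difference there may also reflect the device's own effect on emptying, and it says nothing about fatigue or practice.
2. **Drop counterbalancing.** If the standard exam must come first, for example because it is also the diagnostic exam, delete the counterbalancing statement and state that device and order are confounded. The documents do not settle whether this applies.

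The first option costs a short amendment to Methods and Analyses, a 16-line sequence list and a little more analysis. It keeps the same two exams and the same films per patient, provided that no separate standard exam is needed beforehand for diagnosis.

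### Exam order is randomised and counterbalanced, but the planned signed-rank test ignores it and loses power if order matters

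*Combined protocol and SAP*

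**What the plan says.** The Sample size paragraph describes "16 patients randomly, counterbalanced to both standard toilet seat and CAD", a two-period crossover with randomised order. It does not state the split between the two orders. The number of patients "was considered sufficient to evaluate potential for further study of the current version of the CAD device"; no alpha, power, effect size or SD is given.

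Methods instils 180 ml of barium paste for the standard commode exam, then "additional barium paste (same quantity) instilled in the rectum for a repeat exam". It mentions no clearing step, no interval and no measurement of residue between the exams. It also describes the second instillation as being "for a repeat exam (same 5 spot radiographs) using the commode assist device", which reads as standard commode first and device second.

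The Analyses paragraph compares anorectal angle, perineal descent and rectal emptying between seats, and adds Likert ratings for each condition. "Statistical comparisons will be completed using non-parametric Wilcoxon signed-rank test for repeated measurements". It has no term for exam order and gives no formula for rectal emptying. It leaves the decision on further study or redesign to expert opinion.

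**The concern.** The second exam differs from the first in more than the seat. The patient has already strained and evacuated once. If any paste remains, the second exam also starts from a larger volume. The Background describes the condition as "leading to refractory evacuation", so incomplete emptying in the first exam would not be surprising. Either mechanism can shift second-exam readings for both seats.

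Randomising the order guards against that shift, but the named analysis makes no use of it. The CAD-minus-standard differences then centre on two different values, one for each order. The signed-rank test treats the gap between them as random noise. At stake is the ability of a 16-patient study to see a device effect in its supporting tests.

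**Working it through.** **Inputs.** From the documents: 16 patients, both seats in each patient, random counterbalanced order, 180 ml per exam, signed-rank test. Assumed, because the documents give no figures: 8 patients per order, normal paired differences with SD 1 within each order, two-sided 5% level, true effect δ = 0.78 SD, and order effects π of 0 to 1.0 SD. The plan has no power figure to reproduce. The value 0.78 SD was chosen because it gives about 80% power when there is no order effect.

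**Model.** Let π be the amount by which a second exam reads higher than a first, whichever seat is used.

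| | Standard first | CAD first |
|---|---|---|
| CAD minus standard | δ + π | δ − π |
| Second minus first | δ + π | −δ + π |

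**Bias.** With 8 per order, the mean CAD-minus-standard difference is [(δ + π) + (δ − π)]/2 = δ. The order effect cancels.

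**Spread.** The pooled SD becomes √(1 + π²): 1.03, 1.12 and 1.41 at π = 0.25, 0.5 and 1.0. The standardised effect of 0.78 falls to 0.76, 0.70 and 0.55.

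**Order-based comparison.** The second-minus-first differences in the two orders are separated by (δ + π) − (−δ + π) = 2δ. The order effect drops out, and half the shift estimates δ.

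**Simulated rejection rates.** Exact signed-rank test (reject if the smaller rank sum is 29 or less; actual level 4.4%) against exact rank-sum test, 8 v 8 (reject if a group's rank sum is 49 or less, or 87 or more; actual level 5.0%):

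| Order effect (SD) | Power, pooled signed-rank | Power, order-based rank-sum | Type I error, pooled | Type I error, order-based |
|---|---|---|---|---|
| 0 | 80% | 80% | 4.4% | 5% |
| 0.25 | 78% | about 80% | 3.9% | 5% |
| 0.5 | 71% | 80% | 2.5% | 5% |
| 1.0 | 45% | 80% | about 0.5% | 5% |

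**Rectal emptying.** The effect of residue depends on the missing formula. Suppose 40% is retained in each exam (an assumption). Exam 2 starts at 180 × 1.4 = 252 ml, ends at 0.4 × 252 = 100.8 ml, and evacuates 151.2 ml. The true fraction emptied is 60%. Three possible scores for exam 2 are:

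- 1 − left/180 = 1 − 100.8/180 = 44%, which is 16 points too low.
- Evacuated/180 = 151.2/180 = 84%, which is 24 points too high.
- Evacuated/own starting content = 151.2/252 = 60%, which is correct.

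If instead a constant volume empties (108 ml each time), the third score gives 108/180 = 60% in exam 1 and 108/252 = 43% in exam 2. It then creates an order effect of its own.

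**The case against.** A reader might infer that leftover paste biases the seat comparison. The documents do not support that as stated. They say neither that paste remains nor that it is removed. The 16-point error above is a reading error within one exam. With equal seats and balanced order it falls on both seats alike and cancels, and its sign changes with the formula chosen. Bias under counterbalancing needs carry-over that differs by seat, which an order-based test would not remove either.

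A reader might also infer that false positives are inflated. With balanced order the reverse holds: the pooled test becomes conservative. If the CAD were always second, a 0.5 SD order effect would give about 43% false positives. That figure belongs to a fixed order, which contradicts the Sample size paragraph, and the rank-sum comparison could not be run there because only one order group would exist.

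It is also fair to say that small order effects cost little (about 2 points at 0.25 SD), that the plan claims no power, that its stated aim is perineal descent, and that expert opinion decides the next step. The simulation uses normal data and does not carry over directly to tied Likert ratings. All of this stands and lowers the stakes. It does not make an order-blind test the right match for a design that randomises order, when the matching test costs essentially no power if order turns out not to matter.

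**Conclusion.** The point holds as a mismatch between design and analysis. Order is randomised and counterbalanced, but the named test discards it. The consequence is lost power, not bias or excess false positives: about 2, 9 and 35 points at order effects of 0.25, 0.5 and 1.0 SD, from a starting power of 80%. These figures rest on the assumed 8/8 split, normal differences, the 0.78 SD true effect and the 5% level. The size of any real order effect is unknown. The undefined emptying measure is a secondary matter. The two descriptions of exam order are a separate inconsistency on which any order-based analysis depends.

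**What to change.** 1. **Reconcile exam order.** Make the Sample size and Methods paragraphs agree, and state the split between orders. The analysis below presupposes the randomised order. If the CAD were always second, device and order would be confounded and no order-based analysis could separate them.
2. **Analyse by randomised order group.** Replace the pooled signed-rank test with an exact rank-sum test of second-minus-first differences between the two orders. For Likert items, use a tie-corrected or permutation version.
3. **Report estimates.** For continuous outcomes, give half the Hodges-Lehmann shift between orders, with its 95% CI (limits also halved), as the CAD effect. Report the estimated order effect beside it.
4. **Define emptying (secondary).** Where the spot films can quantify contrast, which the documents do not establish, score emptying as the rest-film content minus the post-evacuation content, divided by the rest-film content of the same exam. Do not divide by the 180 ml instilled. Note that this removes the artefact only if roughly a constant fraction empties.
5. **State the limitation.** Carry-over that differs by seat is not removed.

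The cost of items 2 to 5 is analysis wording. They need no extra patients, films or radiation and no change to paste quantity or procedure. With no order effect, the two tests have about the same power (80% each).

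### The plan makes no provision for masked film reading, or for keeping the expert efficacy judgement apart from knowledge of the seat, although the proposal already calls a support device efficacious

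*Combined protocol and SAP*

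**What the plan says.** The document is a single combined protocol and SAP.

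- **Methods.** Each patient is examined on the standard commode and again on the device. Each exam gives "five standard radiographic spot films including images at rest, with squeeze, with strain, during evacuation and post-evacuation".
- **Sample size.** "A sample size of 16 patients randomly, counterbalanced to both standard toilet seat and CAD was considered sufficient". Each patient therefore contributes one pair, and seat order is counterbalanced.
- **Analyses.** The standard seat is the comparator, and the film outcomes are "differences in anorectal angle, perineal descent, and rectal emptying during the clinical maneuvers at rest, with squeeze, and with straining". Patients also give three Likert ratings per seat. The comparisons use the Wilcoxon signed-rank test, but the decision does not rest on it: "determination of sufficient efficacy for further study and potential redesign will be based on expert opinion of clinical observations".
- **Aim.** The device comes from a collaboration that includes the institution's own engineers: "a pelvic floor support device has been designed, and is ready to be tested".
- **Summary.** Before any testing, a support device is described as cost effective, safe and efficacious, followed by "This has substantial marketability".

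No section names the film reader, the number of readers, a measurement rule, masking or coding of films, or the identity and independence of the experts.

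**The concern.** Measuring anorectal angle and perineal descent means placing landmarks on an image, so the reader's judgement enters the data. The only other outcomes listed in Analyses are ratings by patients, who know which seat they used. The film measurements are thus the one set of outcomes that could be protected from expectation, and the plan does not protect them. The next step, the efficacy judgement, is also a matter of opinion, with no threshold and no separation from the seat.

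The proposal states a favourable view of the device in advance. Counterbalancing deals with order effects and does nothing about a reader who expects one seat to look better.

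At stake is the study's stated purpose, which is deciding whether the current version of the device merits further study or needs redesign. An expectation effect in reading or in judgement could tilt that decision, and nothing in the plan would detect it.

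**Working it through.** **The plan's own figure.** The sample size of 16 cannot be reproduced, because the document gives no significance level, sidedness, power, effect size or SD. For reference, assuming two-sided 5% and 80% power, the paired formula gives a detectable effect of (1.96 + 0.84)/√16 = 0.70 SD of the paired difference (0.75 by the noncentral t).

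**Inputs for the illustration**
- From the document: 16 pairs (Sample size) and the Wilcoxon signed-rank test (Analyses).
- Assumed: two-sided 5% level, normally distributed paired differences, zero true effect, and a constant reading shift b in favour of the device, in SDs of the paired difference. The document gives no reader-error figure, so a range of b is shown.

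**Step 1. Scale.** The standard error of the mean paired difference is SD/√16 = 0.25 SD. Shifts of 0.10, 0.25 and 0.50 SD are therefore 0.4, 1 and 2 standard errors.

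**Step 2. Exact test.** The rank sum totals 16 × 17/2 = 136. The largest critical value with at most 2.5% in each tail is T ≤ 29. The actual two-sided level is 4.43%, or 2.2% in each direction.

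**Step 3. Rejection rates with no true effect** (simulation, 200,000 runs per shift)

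| Shift b (SD) | Favouring device | Two-sided |
|---|---|---|
| 0 | 2.2% | 4.4% |
| 0.10 | 5.1% | 5.9% |
| 0.25 | 13.6% | 13.7% |
| 0.50 | 42.8% | 42.8% |
| 0.75 | 76.8% | 76.8% |

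Hand check with a z-test that treats the SD as known:
- b = 0.10: 1 − Φ(1.96 − 0.4) + Φ(−1.96 − 0.4) = 0.059 + 0.009, about 7%
- b = 0.25: 1 − Φ(1.96 − 1) + Φ(−1.96 − 1) = 0.169 + 0.002, about 17%
- b = 0.50: 1 − Φ(1.96 − 2), about 52%

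The pattern is the same. The z-test rates are somewhat higher because that test uses the full 5% and takes the SD as known.

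**Step 4. Break-even.** The rate favouring the device is 42.8% at b = 0.5 and 57.4% at b = 0.6. By interpolation it reaches 50% at 0.5 + 0.1 × (50 − 42.8)/(57.4 − 42.8) ≈ 0.55 SD.

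**Step 5. What the figures do not cover.** They describe one signed-rank test on one film measurement. The plan defines no positive result for the expert decision, so no error rate can be attached to it.

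**The case against.** **Who reads and who judges.** A reader might infer that the films are measured with the seat known, or that the device's designers do the reading or the judging. The document says neither. It shows that the proposing group has an interest, not who reads. This objection stands: the supportable point is that masking and separation are not provided for.

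**The tests do not drive the decision.** The plan sets the Wilcoxon results below expert opinion, so a rejection rate does not show that bias would produce a go decision. This also stands, and the figures are offered only as an illustration. It does not remove the concern, because an opinion without a criterion is no better protected than a test.

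**The bias may be small.** At 0.10 SD the rate moves only from 4.4% to about 6%, and the 43% figure needs a one-directional shift of two standard errors. Nothing in the document locates the true shift. It would also be too strong to conclude that the trial cannot tell a device effect from reader expectation, since an effect large relative to any plausible reading shift would still show.

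**Masking may fail.** The device may be visible on film, and a reader who attended the live fluoroscopy may remember the exam. The document settles neither point. Partial masking still removes label, order and pairing cues, so this limits the remedy without defeating it.

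**Proportion.** This is a 16-patient proof of concept. The consequence is a weaker basis for deciding on further study, not a confirmatory error. That argues for a cheap remedy, which is what is proposed.

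**Conclusion.** The point holds as a missing safeguard. Film measurements that depend on reader judgement feed an efficacy decision that is itself opinion, neither step is separated from knowledge of the seat, and the proposal anticipates a favourable answer. With 16 pairs the signed-rank tests are sensitive to a systematic reading shift: about 6%, 14% or 43% false rejection at 0.10, 0.25 or 0.50 SD, against 4.4% with none. Those rates assume the shift, normal differences, a two-sided 5% level and no true effect.

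The document does not support saying that bias has occurred or will occur, that the designers read the films, or that these percentages are the chance of a wrong decision to proceed. The change should be made because it is a concrete protection at low cost, whatever the true size of the shift.

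**What to change.** Add to Analyses:

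> The films will be measured as 32 coded exam sets (16 patients × 2 seats) in random order, with seat, patient and exam-order labels removed and images cropped to the anatomy where feasible, by a reader who did not attend the exam where the existing team allows. The reader will record whether the seat was evident. All measurements will be locked before unmasking, and the experts will first review the locked, coded measurements before seat is revealed.

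Whole exam sets are preferable to shuffling all 16 × 2 × 5 = 160 single films, because descent may be taken as change from rest and emptying may need films from the same exam to be compared.

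Report how often the seat was evident, as a limit on the masking. Do not repeat the main comparison on films where it was not evident. That would break pairs and select on a feature that arises after seat assignment. It could also leave too few pairs: with 5, the smallest possible two-sided signed-rank p-value is 2/2⁵ = 0.0625.

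The cost is a few hours of film coding, with no additional patient, procedure or radiation and no requirement for an extra reader. The downside is that masking may be only partial if the device shows on film. The patients' own ratings cannot be masked and are unaffected.

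### The Risks section calls every procedure standard practice although the CAD is still to be tested, and the supplied text names no device risk and describes no structured recording of device problems

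*Combined protocol and SAP*

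**What the plan says.** All references are to the combined protocol and SAP.

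- **Risks** opens with "All procedures are the standard of practice at Mayo Clinic Arizona". It then addresses the second exam only for its exposure: "The radiation used for the additional exam is considered very low, and should not present a hazard to patients", with a pointer to a dosimetry attachment. Premenopausal women take a urine "pregnancy test, and if positive would be excluded from the study as is required by our standard clinical protocols". No other risk is mentioned.
- **Aim** gives the status of the device: "a pelvic floor support device has been designed, and is ready to be tested".
- **Methods** describes the exam on the standard commode and then the second one, on the CAD: "The patient would have additional barium paste (same quantity) instilled in the rectum for a repeat exam (same 5 spot radiographs) using the commode assist".
- **Sample size** gives the purpose as "to evaluate the feasibility of the CAD for patient use, effectiveness, and satisfaction", in 16 patients studied on both seats.
- **Analyses** lists three imaging outcomes (anorectal angle, perineal descent, rectal emptying) and three Likert items (straining, ease of evacuation, completeness of evacuation). It leaves the judgement on further study and possible redesign to experts, on the basis of what they observe clinically.
- **Summary** says that a support device "is a cost effective, safe and efficacious solution".

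**The concern.** A statement that everything done to the patient is standard practice cannot cover a device that the same document presents as awaiting testing. A reviewing board that relied on this sentence would see no device-specific risk to weigh, because none is named.

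The gap also affects the data. The study is partly about whether patients can use the device and whether it needs redesign. Discomfort, injury, a part that slips or fails, and an exam that has to be abandoned are direct evidence on both questions. If no variable is set up for them, such events may be noticed in the room but will not be counted in the same way for each patient and each seat. The study could then end with comparisons of descent and emptying and no usable statement on how the device was tolerated, while the Summary already describes such a device as safe.

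**Working it through.** **1. Does the Risks sentence fit the rest of the document?**

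- Defecography with barium paste and five spot films: the documents treat this as standard clinical practice, and nothing contradicts that.
- The CAD: the Aim says it is ready for testing. The Risks sentence has no exception for it, so as written it covers something it cannot describe.
- The second exam: the type of procedure may well be standard. What is added for the study is the repeat itself, with its second instillation and five more films. Risks openly calls it additional, so this is not a contradiction, but it should be labelled as a research component.

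**2. Which purposes and claims have a variable behind them?**

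- Effectiveness: three imaging outcomes, plus the Likert items.
- Satisfaction: the three Likert items, in part.
- Feasibility of patient use: ease of evacuation bears on it indirectly. Nothing records whether the exam could be completed on the device or whether the device worked.
- Redesign: expert opinion on clinical observations, with no listed malfunction or discomfort item.
- Safety, as asserted in the Summary: no variable and no criterion.

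The count is 3 imaging + 3 Likert = 6 outcomes, of which 0 record a harm, a malfunction or completion.

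**3. What would recording give with this sample?**

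The plan's own figure is 16 patients. It cannot be reproduced, because no alpha, power, effect size or standard deviation is given; it rests on judgement. Taking it as fixed, and assuming that all 16 patients start the exam on the CAD and none has an event, the exact upper limit for the true rate is 1 − a^(1/n):

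- two-sided 95%: 1 − 0.025^(1/16) = 0.206, about 21%;
- one-sided 95%: 1 − 0.05^(1/16) = 0.171, about 17%.

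The chance of seeing at least one event is 1 − (1 − p)^16. The documents give no event rate, so the rates below are assumptions:

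- p = 1%: 14.9%
- p = 2%: 27.6%
- p = 5%: 56.0%
- p = 10%: 81.5%

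Sixteen exams would therefore probably reveal a problem that affects one patient in ten and probably miss one that affects one in a hundred. That makes recording worthwhile for feasibility and redesign, and it limits what can be said about safety.

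**The case against.** The best defence is that this is a short proposal for a proof-of-concept study. Its Risks sentence can be read as referring to the imaging, it discloses the additional exam, and its go-or-redesign decision rests on clinical observation, where a malfunction or an abandoned exam could surface. Part of this stands. Loose wording is a fair description of the sentence, and expert observation is not nothing. But the sentence has no exception for the device, and informal observation is not a variable counted for each exam.

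A reader might also infer several stronger things that the documents do not support:

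- *That the additional exam contradicts the standard-practice statement.* Repeating a standard procedure does not change its type.
- *That this is the first test of the device.* The Aim says only that it is ready to be tested, and the Sample size section speaks of its current version, so earlier versions or earlier testing are possible. No regulatory status is given either.
- *That device risks were left out because the device was taken to be standard practice.* The omission is in the text; the reason is not.
- *That harms will not be recorded at all.* Consent pages were removed and the dosimetry attachment was not supplied. What is shown is that the supplied text describes no structured recording.
- *That the trial plans to conclude that the device is safe.* The word occurs in the closing Summary as an assertion about the concept. Safety is not an objective, and no safety analysis is planned.

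The upper limits of 17% and 21% are also no measure of this plan's defect. They hold for any series of 16 without an event. They show how far a safety statement could go once data exist. The cost-effectiveness wording in the same Summary sentence is a separate matter and is not part of this point.

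**Conclusion.** The point holds in a limited form. The blanket sentence in Risks does not fit a device described as ready for testing. The supplied text names no device-specific risk, and none of the six listed outcomes captures discomfort, injury, malfunction or an uncompleted exam. The plan as described would therefore give no structured safety data and little direct evidence for its own feasibility and redesign purposes, and the Summary's word safe has no planned data behind it.

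This should be corrected, but it does not undermine the paired comparison of descent, angle and emptying. The conclusion assumes that no recording procedure sits in material that was not supplied. The limit of about 21% further assumes 16 exams started on the CAD, no events, and one exam per patient on each seat. Recording would not make the claim of safety true; it would replace an unsupported word with a count and an interval.

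**What to change.** 1. Reconcile Risks with the Aim. Limit the standard-practice statement to the defecography procedure, and identify the CAD, and the repeat of the exam for research, as research components. Name the device-specific risks that the sponsor foresees.
2. After each exam on each seat, complete one short form with four items: pain or discomfort, injury, device malfunction, and whether the exam was completed.
3. Report counts for each seat over exams started on that seat, with exact 95% confidence intervals. Use exams started and not a fixed 16, because a patient may not begin or finish the second exam.
4. Reword the Summary so that safety is not asserted beyond those data. If no event occurs in 16 exams, give the upper limit of about 21% with the statement.

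The cost is an amendment to a few sentences, a one-page form and a safety statement less favourable than the present one. Sample size, imaging procedures and the planned signed-rank comparisons do not change.
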